Safety: All subjects who meet the screening eligibility criteria for the study and receive at least one application of Study drug will be evaluated for safety. The following safety parameters will be assessed: 
• Incidence of adverse events (AEs) throughout the study:
○ A subject-by-subject treatment-emergent AE (TEAE) data listing, including verbatim term, preferred term, treatment, severity, and relationship to the Study drug, will be provided.○ The number of subjects experiencing AEs and number of AEs will be summarized by treatment using frequency counts.○ AEs will not include expected local skin reactions such as: minor pain, small blisters, pruritus, erythema, and post-inflammatory pigment changes.○ Reactions to drug administration will be considered an AE if:
▪ Individual blisters develop that are greater than 20mm in diameter. An aggregated blister composed of a number of smaller blisters is not considered an AE.▪ Any medical intervention excluding administration of mild over-the-counter (OTC) pain relievers is required.▪ The event results in discontinuation from the study.

STUDY SYNOPSIS (continued)

Name of sponsor company: Verrica Pharmaceuticals, Inc.
Name of finished product: VP-102 (0.7% w/v cantharidin delivered via a single-use applicator)
Name(s) of active ingredient(s): Cantharidin

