- a. Screening can occur up to 14 days prior to Study drug application on Day 1. Screening can occur on the same day as treatment Day 1/Study drug application. An IRB-approved ICF must be signed before any study specific procedures are performed.
- b. Subjects may be scheduled 21+/- 4 days after treatment in the event of scheduling conflict. If possible the next treatment or study visit should be scheduled 21 days from the day of the subject's last study visit. The 24 hour follow-up may be conducted at +/- 3 hours. Study medication should be removed after the 24 hour draw is completed.
- c. At end of the study (EOS, ~Day 84), all subjects with unresolved molluscum lesions or unresolved treatment-emergent AEs, will be treated by the investigator per local standard of care. Patients who clear all lesions at study visits prior to ~Day 84 will complete all study related assessments that were required at the EOS visit and will not need to return for further assessment. A study completion form will be completed on the day they are cleared.
- d. Confirmation of eligibility criteria.
- e. Demographics: date of birth, sex, race/ethnicity will be collected.
- f. Vital signs (e.g., temperature & heart rate) will be obtained at screening and at each treatment prior to application of Study drug.
- g. Limited physical examination. Symptom- or AE-directed physical examination may be performed if warranted. (See Source/CRF for further outline of assessment.)
- h. Regional lesion counts (head/neck, trunk, upper/lower extremities) should be performed.
- i. LSR assessment will be performed by the Investigator or trained personnel with a protocol-specific LSR form at each treatment visit and the EOS visit.
- j. CDLQI assessment to be completed prior to Study drug application and at EOS visit. CDLQI must be repeated if the first treatment is not completed within 7 days.
- k. To be performed prior to Study drug application and at EOS in any females of childbearing potential (females that are capable of menstruating).

- l. Photography of molluscum lesions will occur at selected clinical sites only.
- m. Study drug may be gently removed from individual lesions prior to 16 hours of application in the event of significant blistering, significant pain or treatment emergent AEs. Study drug should not be removed from the remaining unproblematic lesions until the 24 hour time point is reached. Every effort should be made to complete the PERIT at 24 hours after application.

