Cathcart, et al.^[21] also reported on parental satisfaction, efficacy, and AEs in 54 children (aged 3 months to 13 years old) with molluscum after treatment with cantharidin. Parents reported 96% improvement post-treatment with a 78% satisfaction rating. Overall, 46% of patients experienced AEs, including pain, pruritus, secondary

infection, and temporary hypopigmentation while 9% experienced severe pain. The authors concluded that cantharidin “should be considered a potential frontline treatment” for molluscum.

Silverberg, et al.^[22] conducted a retrospective study to determine the safety, efficacy and parental satisfaction in 300 children (mean aged 4.7 years old) with molluscum after treatment with 0.7% w/v cantharidin. 90% of patients experienced complete clearing, 8% experienced significant improvement and 2% reported that the therapy was ineffective. 92% of patients had blistering, 37% experienced erythema (which lasted up to 3 weeks), 14% had mild to moderate pain, and 8% had a change in pigmentation at the site of application. Importantly, no major side effects or secondary bacterial infections were noted. 95% of parents stated that they would proceed with cantharidin therapy again if necessary.

The above studies provide evidence of the safety, efficacy, and widespread use of 0.7% w/v cantharidin topical solution in the treatment of molluscum in children of all ages, with no serious adverse events reported. However, there is a wide variation in the quality of the research conducted, timing between applications, duration of exposure of lesions to cantharidin and the exact formulations of cantharidin used.

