risk of secondary infection. Band-Aids may be used in the event there is oozing or leaking, at the discretion of the parent. After the treatment session, parents/guardians will be contacted by the investigator or clinical research team the next day to ensure that application sites have been washed, to discuss responses on the PERIT assessment, and to answer any questions or concerns. Participants will be given a 24-hour call number for any emergencies that may arise post-treatment and throughout the study.

All serious and/or severe AEs will be reported to the IRB and FDA per applicable guidelines and regulations.

3.3

STORAGE AND HANDLING OF INVESTIGATIONAL PRODUCT

Each applicator will be individually wrapped in a labeled Tyvek pouch. This Tyvek pouch should not be opened until you are ready to initiate treatment. The applicator will be labeled with the Investigational New Drug application number and a study identification number. The label will also display the date of production manufacture and the statement “Caution: New Drug--Limited by Federal Law to Investigational Use.” and “Warning: Flammable Liquid.” The applicator will also display warnings appropriate to the characteristics of the Study drug the specifically appropriate yellow triangular flammable symbol sticker with the phrase “Warning: Flammable Liquid” and a yellow toxic chemical symbol with the phrase “Warning: Highly Toxic” as well. Applicators will be received in bulk supply and numbered in sequential order. Applicator numbers are used for accountability purposes only and are recorded on the accountability log as they are used. Applicators do not need to be used in sequential order. All used and unused study product is to be held until completion of the study.

Drug accountability will be reviewed and confirmed by the study monitor assigned by Verrica Pharmaceuticals, Inc., and instructions for destruction or return will be given at that time.

Study drug must be stored at controlled room temperature (68°-77°F; excursions of 59°-86°F are acceptable for short periods) in a secure, dry location with limited and controlled access, and out of direct sunlight. Extended exposure to extreme temperature conditions should be avoided (eg. Study drug should not be left in an unoccupied vehicle). Contact the study sponsor in the event you believe that any materials may have been exposed to such conditions for guidance. Study drug may be

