Adverse event means any untoward medical occurrence associated with the use of a drug in humans, whether or not considered drug related.

An AE can be any unfavorable and unintended sign, symptom, or disease (new or exacerbated) temporally associated with the use of the investigational product, regardless of whether it is considered to be related to the investigational product.

The following are examples of AEs:

- Exacerbation of a chronic or intermittent preexisting condition, including an increase in frequency or intensity of the condition
- New conditions detected or diagnosed after investigational product administration, even if they were present before the start of the study
- Signs, symptoms, or the clinical sequelae of a suspected interaction with another medical product

Examples of AEs do not include the following:

- Medical procedures (The medical condition that led to the procedure as the AE should be reported.)
- Situations that are unwanted by the subject but in which an untoward medical occurrence did not occur, for example social inconvenience after admission to a hospital
- Anticipated day-to-day fluctuations of a preexisting disease or condition (present or detected before enrollment) that does not worsen overall

- Expected progression of the disease being studied, including signs or symptoms of the disease, unless progression is more severe than expected for the subject's condition

AEs may include pretreatment or post treatment events that occur as a result of protocol-mandated procedures (e.g., invasive procedures, modification of the subject's previous therapeutic regimen). AEs should be captured even if they occur during periods without drug treatment or post treatment periods. AE collection begins once the patient has signed informed consent and will continue until the EOS visit has been completed.

The investigator is responsible for performing periodic and special assessments for AEs. The investigator and study personnel will note all AEs mentioned by the subject starting from the day the informed consent is signed and during administration of the investigational product, until the end of study visit (Day 84). All clinical complaints volunteered by or elicited from the subject or parent/guardian during the study will be recorded on the appropriate page of the eCRF for the study period indicated. The subject and parent/guardian will receive appropriate treatment and medical supervision for any AE that occurs.

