5.4 ASSESSMENT OF INTENSITY

The investigator will assess the intensity for each AE and SAE reported during the study. The assessment will be based on the investigator's clinical judgment.

The classifications in [Table 1](#) should be used in assigning intensity of each AE recorded in the eCRF.

Table 1. Classification of AEs by Intensity^a

Intensity	Definition
Mild AE (Grade 1)	An event that is easily tolerated by the subject, causing minimal discomfort and not interfering with everyday activities
Moderate AE (Grade 2)	An event that is sufficiently discomforting to the extent of interfering with normal everyday activities
Severe AE (Grade 3)	An event that prevents the subject from performing normal everyday activities
Life-threatening or disabling AE (Grade 4)	An event that, at the time of occurrence, put the subject at risk of death or resulted in a persistent or significant disability or incapacity
Death related to AE (Grade 5)	An event that resulted in death

AE: adverse event.

a From Common Terminology Criteria for Adverse Events (CTCAE), Version 4.0.

Any AE that changes in intensity or grade during its course will be recorded in the eCRF at the highest level experienced by the subject.

An AE that is assessed as severe should not be confused with an SAE. Severity is a category used for rating the intensity of an AE (such as mild, moderate, or severe myocardial infarction). However, the event itself may be of relatively minor medical significance, such as a severe headache. Both AEs and SAEs can be assessed as severe. An AE is considered serious when it meets one of the predefined outcomes described in [Section 5.2](#).

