11.4. Patient Evaluation of Response to Treatment (PERIT)

Twenty-four (24) hours after each treatment, an assessment of treated skin appearance will be carried out. Possible assessments include: No Response, Redness Only, Blistering at application site, Excessive blistering at application site and beyond.

Overall counts and percentages will be displayed by treatment group for each treatment visit. In addition, a summary of the highest severity will be shown.

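### No AE trigger for drug reactions uses the intensity scale, and protocol and SAP disagree on whether local skin reactions are AEs, so a severe reaction, above all pain, may go unrecorded

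*Protocol*

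**What the plan says.** **Protocol synopsis, Criteria for evaluation, Safety.** Expected reactions are set aside: "AEs will not include expected local skin reactions such as: minor pain, small blisters, pruritus, erythema, and post-inflammatory pigment changes". A reaction becomes an AE if a single blister exceeds 20 mm, if it leads to discontinuation from the study, or if this holds: "Any medical intervention excluding administration of mild over-the-counter (OTC) pain relievers is required".

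**Protocol Sections 2.1 and 2.3.1.** LSRs are declared not to be AEs, without a severity limit. The signs to be recorded are erythema with swelling, flaking or scaling, dryness, and scabbing or crusting, plus pigment change and scarring. Pain and blistering are not listed.

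**Protocol Section 5.1.** The general definition is wide: "Adverse event means any untoward medical occurrence associated with the use of a drug in humans, whether or not considered drug related". The same section requires clinical complaints, volunteered or elicited, to be recorded.

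**Protocol Table 1 (Section 5.4).** Grade 3 is defined by function: "An event that prevents the subject from performing normal everyday activities".

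**Protocol Section 3.2.** "All serious and/or severe AEs will be reported to the IRB and FDA per applicable guidelines and regulations".

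**SAP Sections 3 and 11.3.** LSRs will be recorded as AEs, with blistering and pain named and no threshold set. They are picked out by medical review of the AEs reported, then summarised by preferred term and highest severity.

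**The concern.** The trigger list looks at blister size, at the treatment given and at discontinuation. It does not ask how bad the reaction was on the protocol's own scale. Two children with equally disabling pain could be recorded differently because one family used a mild pain reliever at home and the other sought care.

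The SAP assumes that LSRs arrive in the database as AEs. The protocol that sites work from tells them LSRs are not AEs. If sites follow the protocol, the SAP's severity tables for AEs and LSRs (Sections 11.2 and 11.3) rest on a selected set of events, and the severe-event reporting in Protocol Section 3.2 is not set in motion. At stake is the count of severe reactions in children treated with a blistering agent, where tolerability is part of a stated secondary objective.

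**Working it through.** The plan gives no figure to reproduce. The check is a test case read against the text, followed by an illustration of scale.

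**1. Test case.** A child has pain meeting Grade 3 and no single blister above 20 mm. The family gives a mild over-the-counter pain reliever, washes the lesion early, and the child stays in the study.
- Blister trigger: not met.
- Intervention trigger: the pain reliever is expressly excepted. Whether early washing is a medical intervention is not defined. Sections 4.2.2 and 4.2.3 let the family do it at home, so the natural reading is that it is not.
- Discontinuation trigger: not met.

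**2. Remaining protocol text.**
- Toward not recording: Sections 2.1 and 2.3.1 on LSRs. Also, the synopsis sets no limit on the exclusion of pruritus, erythema or pigment change.
- Toward recording: the synopsis excludes only minor pain and small blisters, and Section 5.1 is broad.
- Result: two sites could handle the same child differently, each with text to cite.

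**3. Whether the SAP restores the event.** Section 11.3 finds LSRs among AEs already reported, so an event never entered cannot be found. Protocol Section 7.2 allows the SAP to modify the analysis plan. It does not say that the SAP changes what sites record or report.

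**4. Other graded sources.**
- Blistering: the SAP's LSR form (Section 11.3) grades it, and the parent's next-day form (PERIT, SAP Section 11.4) has these categories: "No Response, Redness Only, Blistering at application site, Excessive blistering at application site and beyond". The SAP places the LSR form at 1, 7 and 14 days after each treatment and at the end-of-study visit. The protocol schedules LSR assessment only at treatment visits and end of study.
- Pain: absent from the protocol's LSR list, from the SAP's graded form and from PERIT. The content of the Safety Monitoring Questionnaire is not given. On the text available, a pain grade depends on AE entry.

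**5. Scale, as illustration only.** Inputs:
- n = 32 (16 exposure plus 16 standard) or n = 40 (maximum enrolment).
- p = 0.09, from a retrospective series of 54 children in Protocol Section 1.2.2 ("while 9% experienced severe pain"). Assumption: this rate carries over per child, and its severe pain matches Grade 3.
- s = share of such reactions that escape recording. Not given; range 0 to 1.

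Expected children with severe pain, n × p:
- 0.09 × 32 = 2.9
- 0.09 × 40 = 3.6

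Chance of at least one, 1 − (1 − p)^n:
- 1 − 0.91^32 = 0.951
- 1 − 0.91^40 = 0.977

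Expected number missed, s × n × p: from 0 to 2.9 (n = 32) or from 0 to 3.6 (n = 40).

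Upper 95% limit if none is recorded:
- One-sided, 1 − 0.05^(1/n): 8.9% (n = 32), 7.2% (n = 40)
- Two-sided, 1 − 0.025^(1/n): 10.9% (n = 32), 8.8% (n = 40)

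**The case against.** The strongest case against is that the plan already captures these reactions. The SAP says LSRs, pain included, are recorded as AEs with no threshold. If that governs, the trigger list gates nothing. The synopsis says a reaction is an AE if a trigger holds, not only if one does; it sets aside only minor pain and small blisters; and Section 5.1 covers the rest. The 20 mm limit is itself a rough severity test for blisters. The pain reliever would appear in the concomitant-medication record with its reason (Protocol Section 3.4).

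Much of this stands. It defeats the reading that the protocol excludes severe reactions from AEs. A reader might infer that exclusion from footnote m of the schedule, which allows early removal "in the event of significant blistering, significant pain or treatment emergent AEs". But items in such a list can overlap, and Sections 3.2 and 4.2.2 tie removal at 24 hours to the absence of adverse events or adverse reactions. The footnote proves little either way. It is also true that the gap is mainly about pain, since blistering has graded sources.

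Two things remain. The SAP's statement directly contradicts Protocol Sections 2.1 and 2.3.1, and it acts only on events already entered. A concomitant-medication entry carries no intensity grade and does not lead to reporting under Section 3.2.

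**Conclusion.** The point holds as an ambiguity in recording combined with a protocol-SAP conflict. No trigger uses a Table 1 grade. The two documents disagree on whether LSRs are AEs, and pain has no graded source in the text outside AE entry. A Grade 3 reaction managed at home may therefore go unrecorded, and any such loss can only lower the severe counts.

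The size cannot be fixed. With 9% assumed, the expected number missed lies between 0 and 2.9 of 32, or 0 and 3.6 of 40. The 9% comes from one small series of another cantharidin preparation. The protocol's interim account of VP-102 (14 and 12 subjects) reports no treatment-related AEs, and its 300-child series reports only mild to moderate pain.

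Two stronger readings are not supported:
- That the severe rows will read zero. This needs every case to escape both the triggers and the general definition.
- That a zero would rule out 9%. At n = 32 the one-sided limit of 8.9% only just falls below 9% and the two-sided limit of 10.9% does not. The SAP's safety section specifies no confidence interval.

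**What to change.** 1. Reconcile the synopsis and Protocol Sections 2.1 and 2.3.1 with SAP Sections 3 and 11.3, by protocol amendment where site instructions change, so that sites record what the SAP will tabulate.
2. State in the synopsis list and in Section 2.3.1 that any reaction meeting Table 1 Grade 3 or higher is recorded as an AE with its intensity, whether or not it is an LSR and however it was managed.
3. Ask for the worst pain since application, as a Table 1 grade, at the next-day call already scheduled.

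Early removal of the drug should not be made a trigger. Sections 4.2.2 and 4.2.3 allow it once lesions have blistered, so expected reactions of any severity would become AEs, and recording would again depend on what the family did.

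The cost is one sentence in two places, the reconciling edits, and one line on the call or AE page. Somewhat more AEs and severe AEs will be reported. The change concerns recording only and says nothing about treatment or the timing of removal.

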T24	human bladder carcinoma cells
TSGH 8301	human urinary bladder carcinoma cell line
VP-102	Verrica Pharmaceuticals-102 (0.7% w/v cantharidin)
w/v	weight/volume

1.0 INTRODUCTION

1.1 MOLLUSCUM CONTAGIOSUM

The causative agent of molluscum contagiosum (molluscum) is the molluscum virus, a dermatotropic DNA poxvirus. Molluscum is common in the pediatric population and is prevalent worldwide. It produces small flesh-colored papules and papulovesicles, 1-4 mm in diameter, which typically have an umbilicated or dimpled center. There is often little inflammation associated with molluscum papules, and the presence of an inflammatory reaction to such papules often heralds resolution of the disease. Molluscum lesions are generally not painful, but they may itch or become irritated. Picking or scratching the bumps can lead to autoinoculation, secondary bacterial infection or scarring.

Molluscum is spread readily by autoinoculation and by person-to-person contact. The virus may also be transmitted by touching objects such as towels, clothing, or toys. Most immunocompetent individuals will spontaneously clear the disease in an average of 13 months, although 25% children still have the disease after 18 months.^[3] Spread to siblings and friends, as well as the development of additional lesions in neighboring sites during this time causes parental angst, socialization challenges for the afflicted individuals^[1, 2] and has been shown to negatively impact quality of life.^[3] The highest incidence is in children up to 14 years of age, where the incidence rate ranges from 12 to 14 episodes per 1000 children per year.^[4]

There is no approved product by the Food and Drug Administration (FDA) for the treatment of molluscum. Given that there are no approved options, physicians employ a variety of treatment approaches including (a) benign neglect; (b) curettage; (c) cryotherapy; (d) expressing the molluscum bodies; (e) retinoic acid creams; (f) caustic agents; (g) topical immunotherapeutics; and (h) non-standardized, compounded cantharidin products of various purity, formulations, and strengths.

1.2 CANTHARIDIN

Cantharidin (1,2-dimethyl-3,6-epoxyperhydrophthalic anhydride) is a lipophilic natural compound that can be isolated from the body fluids of the blister beetle, primarily of the family Meloidae. Blister beetles are found in many parts of the world, including the southern United States and Asia (*Mylabris Cichorii L* and *Mylabris*

phalerata). *Lytta vesicatoria*, a metallic green beetle, was primarily used as a source of cantharidin in the early 1900s, as it is endemic to the United States. Regardless of species of blister beetle, the structure of the cantharidin molecule is maintained with only variations in the quantity of compound that can be readily isolated. The *Mylabris* species of beetle contains a much greater concentration of cantharidin and is the primary type of beetle used in modern cantharidin preparations.

Cantharidin functions as a vesicant, weakening desmosomes in the epidermis when applied topically via a liquid film-forming formulation. Application to the skin causes the release of neutral serine proteases resulting in the destruction of intercellular desmosomes responsible for holding the layers of the skin together.^[5] Intracellular tonofilaments are also weakened, the result being a fluid-filled, thin-walled epidermal vesicle. The superficial nature of the blisters is attributed to cantharidin's lesser effect on hemidesmosomes in the basal layer compared to the more superficial desmosomes. In almost all patients, this process does not cause a scar, as the underlying dermal layer of skin is undamaged. Cantharidin has no known direct antiviral effects.

Many physicians prefer cantharidin to other therapies for the treatment of molluscum such as cryotherapy, curettage or pricking individual lesions with subsequent expression of molluscum bodies because it is painless upon application, requires only limited treatment cycles for significant lesion reduction or complete resolution and is well-tolerated by patients, most of whom are children. Further, cantharidin's long history of use has provided strong evidence of its safety when applied topically.

Although cantharidin has been used extensively for decades in the treatment of several dermatologic conditions including molluscum and verruca vulgaris, specifications for the quality of active pharmaceutical ingredient or a standardized formulation have never been established. Furthermore, a lack of reliable and regulated vendors of the compounded drug increases the chance of the drug product being inappropriately prepared, tested, stored or applied, which in turn increases the potential for unintended or even dangerous consequences in the future. Most currently used cantharidin preparations are prepared as 0.7% w/v (weight/volume) solutions in an acetone solvent with a flexible-collodion base in a screw-top glass bottle at volumes intended for repeated use across multiple patients by the medical professional. This type of container closure system paired with highly volatile formulations presents multiple challenges. Current clinical practice, which reuses the same bottle on multiple patients,

increases the risk of cross-contamination and viral transmission. Furthermore, due to the presence of volatile solvents in the preparation, evaporation from multiple uses heightens the risk of increased concentration and viscosity of the cantharidin in solution and creates a scenario where highly-concentrated material may be applied to the patient's skin. Many formulations also lack formal stability studies and medical professionals often will just use the material until it is "too thick" to apply. As a consequence, many patients are likely receiving much more drug than is clinically necessary to treat their molluscum lesions. While this does provide evidence of the safety profile for the drug, it also introduces unnecessary risk to the patient. Further, the nature of the liquid product coupled with the traditional application strategy of using the wooden end of a cotton-tipped swab makes it difficult to apply the minimum amount of drug necessary to achieve the desired effect. Complete treatment of all lesions is further confounded by the fact that there is no visual indicator present in the formulation to clearly identify for physicians, patients and caregivers where the drug has already been applied during the treatment session.

To address these current shortfalls, Verrica Pharmaceuticals, Inc. has developed VP-102, a 0.7% w/v cantharidin formulation, consistent with the predominant concentration of cantharidin used by physicians. VP-102 is delivered in a single-use glass ampule stored within a single-use plastic applicator with integrated inline filter to remove any glass particles capable of breaking the skin to minimize cross-contamination and concentration changes during use. Each VP-102 applicator will be able to deliver up to 450 μ L (microliters), with each VP-102 unit containing 3.15 mg of cantharidin. Gentian violet, a dye common in surgical markers, has also been included to facilitate physician recognition of treated vs. untreated molluscum lesions. Finally, to afford additional safety and deter potential oral ingestion of the drug by young patients, the oral deterrent denatonium benzoate has been included.

